1.2 Treatment of Relapsed or Refractory Hodgkin Lymphoma

The majority of patients with HL are cured with combination chemotherapy and/or radiation therapy with complete remission attained in >80% of patients. High-dose therapy and autologous stem cell transplant (ASCT) are used as standard of care for patients with primary resistant or recurrent HL. While transplant results in a cure for some patients, more than 50% will eventually relapse and die of the disease (Majhail et al. 2006). Prognostic factors have been identified that affect long-term outcomes after transplant for patients with Hodgkin disease. Time-to-treatment failure has been found to be adversely influenced by advanced stage at diagnosis, complementary radiotherapy before ASCT, a short first complete response, and detectable disease at ASCT (Sureda et al. 2005). Patients who progress after ASCT have limited therapeutic options to improve the outcome of their disease.

1.3 Prognostic Factors in Hodgkin Lymphoma

Prognostic factors have been identified that affect long-term outcome after transplant for patients with Hodgkin disease. Poor outcomes post-ASCT are associated with the presence of B symptoms, extranodal disease, and a less than 12 month duration of remission after frontline chemotherapy. Patients with intermediate or high-risk disease have a 5-year event-free survival (EFS) rate of less than 30% compared to 65% to 80% for patients with low-risk disease (Moskowitz et al. 2001, Majhail et al. 2006), (Sureda et al. 2005). Patients who progress after ASCT have limited therapeutic options to improve the outcome of their disease. Most relapses occur within the first 2 years post-ASCT. Introducing a novel therapy to prevent disease progression and/or relapse in intermediate- to high-risk patients post-ASCT would be of benefit for these patients.

1.4 Post-transplant Therapy for Hodgkin Lymphoma

Based on data in the AETHERA trial, in August 2015 the FDA approved brentuximab vedotin for the post-autologous hematopoietic stem cell transplantation (auto-HSCT) treatment of patients with classical HL at high risk of relapse or progression. Progression-free survival (PFS) in the brentuximab vedotin arm was 42.9 months compared to 24.1 months in the placebo arm (Moskowitz et al. 2015). While leading to a significant improvement in PFS, discontinuation of

CONFIDENTIAL

STUDY DRUG: NIVOLUMAB

SARAH CANNON DEVELOPMENT INNOVATIONS STUDY NUMBER:

FINAL PROTOCOL DATE: 07 FEB 2020

BMT 24

VERSION 7

treatment due to adverse events occurred in over 30% of patients primarily due to peripheral sensory and motor neuropathies (Moskowitz et al. 2015). This intolerance to the only established therapy to prevent relapse demonstrates the need for the development of novel treatment options for these patients.

1.5 Nivolumab

Nivolumab (also referred to as BMS-936558 or MDX1106) is a human monoclonal antibody (HuMAb; immunoglobulin G4 [IgG4]-S228P) that targets the programmed death-1 (PD-1) cluster of differentiation 279 (CD279) cell surface membrane receptor. PD-1 is a negative regulatory molecule expressed by activated T and B lymphocytes (Sharpe et al. 2007). Binding of PD-1 to its ligands, programmed death-ligand 1 (PD-L1) and 2 (PD-L2), results in the down-regulation of lymphocyte activation. Inhibition of the interaction between PD-1 and its ligands promotes immune responses and antigen-specific T-cell responses to both foreign antigens as well as self-antigens. Nivolumab is expressed in Chinese hamster ovary (CHO) cells and is produced using standard mammalian cell cultivation and chromatographic purification technologies. The clinical study product is a sterile solution for parenteral administration.

The pharmacokinetics (PK), clinical activity, and safety of nivolumab have been assessed in subjects with non-small cell lung cancer (NSCLC), melanoma, clear-cell renal cell carcinoma (RCC), and classical Hodgkin Lymphoma (cHL) in addition to other tumor types. Nivolumab monotherapy is approved in multiple countries, including the US and EU, for unresectable or metastatic melanoma, previously treated metastatic NSCLC, and previously treated advanced RCC. In addition, nivolumab is also approved for the treatment of cHL in the US.

1.5.1 Clinical Efficacy

Nivolumab has demonstrated durable responses exceeding 6 months as monotherapy and in combination with ipilimumab in several tumor types, including NSCLC, melanoma, RCC, cHL, SCLC, gastric cancer, urothelial cancer, hepatocellular carcinoma, and colorectal cancer. In confirmatory trials, nivolumab as monotherapy demonstrated a statistically significant improvement in overall survival (OS) compared with the current standard of care in subjects with advanced or metastatic NSCLC, unresectable or metastatic melanoma, advanced RCC, or squamous cell carcinoma of the head and neck (SCCHN).

1.5.1.1 Clinical Efficacy in Hodgkin Lymphoma

Nivolumab monotherapy has demonstrated clinical benefit in subjects with cHL who have relapsed or progressed, including those who received autologous hematopoietic stem cell transplantation and post-transplantation brentuximab vedotin, and has been approved for use in the US. Two studies evaluated the efficacy of nivolumab as a single agent in patients with cHL after failure of autologous HSCT and post-transplantation brentuximab vedotin. Patients received 240 mg of nivolumab administered intravenously (IV) over 60 minutes every 2 weeks until disease progression, maximal clinical benefit, or unacceptable toxicity. A cycle consisted of one dose. Dose reduction was not permitted.

Efficacy was evaluated in 95 patients (both trials combined) who had received brentuximab vedotin after failure of autologous HSCT. Response was assessed using the Revised Response

CONFIDENTIAL

STUDY DRUG: NIVOLUMAB

SARAH CANNON DEVELOPMENT INNOVATIONS STUDY NUMBER:

FINAL PROTOCOL DATE: 07 FEB 2020

BMT 24

VERSION 7

Criteria for Malignant Lymphoma (Cheson et al. 2007). Seven patients (7%) had complete remission (CR) with a 95% confidence interval (CI, [3, 1]) and 55 (58%) patients had partial remission (PR) with a 95% CI (47, 68). The objective response rate (CR + PR) was 62 patients (65%). Median duration of response (DoR) was 8.7 months and median time to response was 2.1 months.

1.5.2 Clinical Safety

The overall safety experience with nivolumab, as a monotherapy or in combination with other therapeutics, is based on experience in approximately 12,300 subjects treated to date. For monotherapy, the safety profile is similar across tumor types. There is no pattern in the incidence, severity, or causality of adverse events (AEs) to nivolumab dose level. In Phase 3 controlled studies, the safety profile of nivolumab monotherapy is acceptable in the context of the observed clinical efficacy and manageable using established safety guidelines. Clinically relevant AEs typical of stimulation of the immune system were infrequent and manageable by delaying or stopping nivolumab treatment and timely immunosuppressive therapy or other supportive care.

1.5.2.1 Renal and Hepatic Impairment

The effect of renal impairment on the clearance (CL) of nivolumab was evaluated in subjects with mild (glomerular filtration rate [GFR] <90 and ≥ 60 mL/min/1.73 m²; n=379), moderate (GFR <60 and ≥ 30 mL/min/1.73 m²; n=179), or severe (GFR <30 and ≥ 15 mL/min/1.73 m²; n=2) renal impairment compared to subjects with normal renal function (GFR ≥ 90 mL/min/1.73 m²; n=342) in the population pharmacokinetic (PPK) analysis. No clinically important differences in the CL of nivolumab were found between subjects with mild or moderate renal impairment and subjects with normal renal function. Data from subjects with severe renal impairment are too limited to draw conclusions on this population.

The effect of hepatic impairment on the CL of nivolumab was evaluated in subjects with mild hepatic impairment (total bilirubin 1.0 to 1.5 times upper limit of normal [ULN] or aspartate aminotransferase [AST] $>$ ULN as defined using the National Cancer Institute [NCI] criteria of hepatic dysfunction; n=92) compared to subjects with normal hepatic function (total bilirubin and AST \leq ULN; n=804) in the population PK analyses. No clinically important differences in the CL of nivolumab were found between subjects with mild hepatic impairment and normal hepatic function. Nivolumab has not been studied in subjects with moderate (total bilirubin >1.5 to 3 times ULN and any AST) or severe hepatic impairment (total bilirubin >3 times ULN and any AST).

1.6 PD-1 Expression in Hodgkin Lymphoma

Studies have found high expression of PD-L1 in HL (Roemer et al 2016). Programmed cell death protein 1 (PD-1) blockade with nivolumab in clinical trials enrolling heavily pre-treated HL patients have resulted in response rates in over 85% of patients (Ansell et al. 2015). The most common drug-related AEs were rash and decreased platelet count with 9% of patients discontinuing due to toxic effects (Ansell et al. 2015). Data demonstrating the tolerability and

CONFIDENTIAL

STUDY DRUG: NIVOLUMAB

SARAH CANNON DEVELOPMENT INNOVATIONS STUDY NUMBER:

FINAL PROTOCOL DATE: 07 FEB 2020

BMT 24

VERSION 7

efficacy of PD-1 inhibition in HL patients make nivolumab a promising therapy to evaluate in the post-transplant setting.

1.7 Rationale for the Study

The malignant Reed-Sternberg cells found in HL have been found to overexpress PD-1 (Green et al. 2010). Nivolumab, an antibody directed against PD-1, has been well-tolerated and efficacious in this patient population (Ansell et al. 2015). We propose to study nivolumab maintenance therapy post-ASCT in Hodgkin disease to see if it is well-tolerated when given as early maintenance therapy. Moskowitz et al. 2010 conducted a study to identify prognostic factors for patients with relapsed or refractory HL receiving transplant. In this analysis of 153 patients, it was found that functional imaging status before ASCT was the only factor significant for EFS and OS and clearly identified a poor risk population (5 year EFS 31% and 75% for FI-positive and negative patients respectively). This study aims to enroll high-risk patients as defined by this manuscript to receive nivolumab therapy as consolidation therapy post-transplant. We are also exploring if PFS can be prolonged in high-risk HL patients compared to historical placebo controls reported in other studies.

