3. STUDY PATIENT POPULATION AND DISCONTINUATION

3.1 Inclusion Criteria

Patients who will receive study drug must meet the following criteria in order to be included in the research study:

1. Patients 18 years of age and older with HL who have received auto-HSCT in the previous 45-180 days.
2. Complete response (CR), partial response (PR) or stable disease (SD) to salvage therapy prior to ASCT
3. High risk of residual HL post-ASCT, as determined by 1 of the following:
 - Positive PET scan defined by the Deauville scale 3-4 (Appendix C) and within 2 months of start of high-dose chemotherapy prior to ASCT
 - Refractory to frontline therapy
 - Relapse <12 months after frontline therapy
 - Relapse \geq 12 months after frontline therapy with extranodal disease
4. Eastern Cooperative Oncology Group (ECOG) Performance Status score of 0 - 1 (Appendix A).
5. Adequate hematologic function defined as all of the following:
 - Absolute neutrophil count (ANC) \geq 1000/ μ L
 - Hemoglobin (Hgb) \geq 8 g/dL (transfusions to reach this point are not permitted)
 - Platelets \geq 50,000/ μ L (transfusion is not permitted)
6. Adequate liver function defined as all of the following:
 - Alanine aminotransferase (ALT) and aspartate aminotransferase (AST) \leq 2.5 \times the upper limit of normal (ULN)
 - Total bilirubin \leq 1.5 \times ULN (unless the patient has Grade 1 bilirubin elevation due to Gilbert disease or a similar syndrome involving slow conjugation of bilirubin)
7. Adequate renal function defined as serum creatinine \leq 1.5 mg/dL (133 μ mol/L)

CONFIDENTIAL

STUDY DRUG: NIVOLUMAB

SARAH CANNON DEVELOPMENT INNOVATIONS STUDY NUMBER:

FINAL PROTOCOL DATE: 07 FEB 2020

BMT 24

VERSION 7

8. Females of childbearing potential must have a negative serum or urine pregnancy test result within 72 hours prior to the first dose of nivolumab and must agree to follow instructions for method(s) of contraception for the duration of treatment with nivolumab and for 7 months following their last dose of study drug (Appendix D). Females of non-childbearing potential are those who are postmenopausal greater than 1 year or who have had a bilateral tubal ligation or hysterectomy.

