7.2 Baseline Study Assessments

The following information will be collected and procedures will be performed for each patient at screening:

- Written informed consent prior to any other study-related procedures (≤ 28 days prior to initiation of treatment)
- Medical history
 - Prior systemic therapy and radiotherapy for HL
 - Results of pre-transplant PET-CT (if done)
- Physical examination, measurements of height (first visit), weight, and vital signs (resting heart rate, BP, respiratory rate, and oral temperature)
- ECOG performance status (see Appendix A)
- 12-lead ECG
- Concomitant medication review
- CBC with 3-part differential and platelets
- CMP to include: glucose, blood urea nitrogen (BUN), creatinine, sodium, potassium, chloride, calcium, carbon dioxide (CO₂), alkaline phosphatase (ALP), AST, ALT, total bilirubin, total protein, and albumin
- Coagulation analysis: PT/INR/PTT
- Serum or urine pregnancy test (must be performed within 72 hours of Cycle 1 Day 1)
- PET-CT scans ≤ 6 weeks prior to initiation of study treatment

CONFIDENTIAL

STUDY DRUG: NIVOLUMAB

SARAH CANNON DEVELOPMENT INNOVATIONS STUDY NUMBER:

FINAL PROTOCOL DATE: 07 FEB 2020

BMT 24

VERSION 7

- Bone marrow biopsy, only if there is prior evidence of bone marrow involvement. If bone marrow biopsy needs to be repeated, it should be done ≤ 28 days prior to initiation of study treatment.

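### Section 1.7 defines the population by pre-transplant imaging, but Inclusion 3 also admits imaging-negative patients; one 50% benchmark, not supported by the protocol's own figures, is applied to all of them

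*Combined protocol and SAP*

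**What the plan says.** Section 1.7 (Rationale) describes a 153-patient analysis in which "functional imaging status before ASCT was the only factor significant for EFS and OS and clearly identified a poor risk population", and gives "5 year EFS 31% and 75% for FI-positive and negative patients respectively". It then states: "This study aims to enroll high-risk patients as defined by this manuscript to receive nivolumab therapy as consolidation therapy post-transplant".

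Section 3.1, item 3, sets a different rule: "High risk of residual HL post-ASCT, as determined by 1 of the following". The first route is imaging: "Positive PET scan defined by the Deauville scale 3-4 (Appendix C) and within 2 months of start of high-dose chemotherapy prior to ASCT". The other three are not: "Refractory to frontline therapy"; "Relapse <12 months after frontline therapy"; and relapse at 12 months or later with extranodal disease. The synopsis gives the same four routes.

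Section 10.2 sets a null of 50% and an alternative of 70% for 12-month PFS, without regard to imaging status. Section 10.4.2 plans Kaplan-Meier estimates at 12 and 24 months and no analysis by pre-transplant PET result. Section 7.2 collects that result only where a scan was done. The five control patients are enrolled to compare immune recovery (Section 5.4.2).

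**The concern.** A patient with a negative pre-transplant scan and, say, an early relapse is eligible, yet falls outside the poor-risk group that Section 1.7 says the trial enrols. The two groups differ by 44 percentage points at 5 years in the protocol's own text. With a fixed external benchmark and no concurrent efficacy comparison, a favourable 12-month PFS could reflect nivolumab, the proportion of imaging-negative patients, or a benchmark that is too low for everyone. The planned analysis cannot separate these.

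**Working it through.** **1. The plan's own figure.** Inputs from Section 10.2: exponential survival, 12-month PFS of 50% against 70%, 18 months' accrual, 12 months' further follow-up, n = 36, two-sided 5%. The hazards are h0 = -ln(0.5)/12 and h1 = -ln(0.7)/12. The event probability under the alternative is 1 - (e^(-12·h1) - e^(-30·h1))/(18·h1) = 0.4579, as stated. That gives 36 × 0.4579 = 16.5 events (stated: 16). Power with the null variance is 80.3%, as stated. The sample-size arithmetic is not in question.

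**2. Do the protocol's figures support 50% at 12 months?** Under the same exponential assumption:

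- Placebo PFS of 24.1 months (Section 1.4), read as a median: 0.5^(12/24.1) = 0.708.
- Imaging-positive, 31% at 5 years (Section 1.7): 0.31^(1/5) = 0.791.
- Imaging-negative, 75% at 5 years: 0.75^(1/5) = 0.944.
- In the other direction, 50% at 12 months implies 0.5^5 = 3% at 5 years.

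The exponential shape matters. Section 1.3 says most relapses fall in the first 2 years, which would lower the 79%. For imaging-positive patients to be at 50% by 12 months, 0.50/0.69 = 72% of their 5-year failures would have to occur in year one. The documents do not say whether that is so. They do not supply the 50% elsewhere either: Section 10.2 calls it a 6-month rate in the next sentence and attributes it to the response criteria, and Appendix F as reproduced contains no PFS rate.

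**3. How far could case mix move the result?** Let w be the imaging-negative share, which is not stated. Assume no drug effect, imaging-positive patients exactly at 50%, and imaging-negative patients at 75% at 12 months. The 75% is the lowest 12-month value compatible with 75% at 5 years, since a survival curve cannot rise. True 12-month PFS is then 0.50(1 - w) + 0.75w. The one-sample log-rank statistic (O - E)/√E against the 50% null was simulated with n = 36 and follow-up uniform over 12-30 months. The range runs from a constant imaging-negative hazard to no imaging-negative events after 12 months.

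| w | True 12-month PFS | Trials declaring benefit |
|---|---|---|
| 0 | 50% | 1.7% |
| 25% | 56% | 14-23% |
| 40% | 60% | 30-51% |
| 50% | 62.5% | 44-70% |
| 60% | 65% | 59-84% |

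If imaging-negative entrants instead share the 50% rate, the figure stays at about 1.7% for every w.

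**4. Would PET-specific nulls of 50% and 75% cure it?** Only if those rates happen to be true. With no drug effect and exponential curves through 31% and 75% at 5 years, a test with those nulls declares benefit in 99% of trials at w = 0, 25% and 50%. With everyone at a 24.1-month median, it does so in about 86%, 60% and 28%.

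**The case against.** The strongest reply is that the imaging-negative patients admitted here are not those behind the 75%. Each must be refractory, early-relapsing or extranodal. Section 1.3 links extranodal disease and a remission under 12 months to poor outcome and gives 5-year EFS below 30% for intermediate- or high-risk disease. No passage gives an outcome for patients who are imaging-negative and also carry one of these factors. This stands. A reader might infer that imaging-negative entrants already exceed the 70% target without nivolumab; the documents do not support that. The 75% covers all imaging-negative patients in the cited series, whose post-transplant treatment is not described.

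The measures also differ. The 5-year figures are EFS and the trial uses PFS. Section 10.4.2 starts PFS at first dose, 45-180 days after transplant, while Section 2.2 speaks of 12 months post-transplant. Section 1.7 does not define a positive scan, Inclusion 3 uses Deauville 3-4, and Appendix F counts score 3 as complete metabolic response. These points limit any numerical carry-over.

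Finally, PFS is secondary, safety is primary, and the log-rank test appears only in the sample-size section; Section 10.4.2 states no success rule. That lowers the stakes. It does not remove the problem, because 50% against 70% is the only efficacy yardstick in the plan.

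None of this answers the mismatch between Section 1.7 and Inclusion 3. The benchmark doubt also reaches imaging-positive patients, so it is wider than case mix.

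**Conclusion.** The mismatch is certain: the rationale names an imaging-defined population and the eligibility rule produces a broader one. The comparison with 50% therefore depends on a case mix that is neither planned nor reported. Separately, the protocol's figures point to roughly 71% (placebo median) or 79% (imaging-positive) at 12 months. Both values rest on the exponential assumption, the second also on treating EFS as PFS, and both would fall if relapse is front-loaded.

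The size of the case-mix effect is unknown. It ranges from none, if imaging-negative entrants do as the imaging-positive do, to 14-84% false declarations of benefit at shares of 25-60%, if they sit at 75% and the imaging-positive at 50%. A reader might go on to set a 75% null for PET-negative patients; the documents do not support that figure for the patients admitted, and it could hide a real benefit if Section 1.3 describes them better. This should be corrected, but it does not undermine the primary safety objective.

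**What to change.** 1. Reword Section 1.7 so that the population it describes is the one Inclusion 3 admits.
2. In Section 10.4.2, add Kaplan-Meier 12-month PFS with 95% CI by pre-transplant PET status (positive, negative, not done), using the results collected under Section 7.2, and state which Deauville scores count as positive for this analysis.
3. In Section 10.2, justify 50% for the population actually admitted, with its source, time point and time origin.
4. State that benefit will not be concluded from the pooled comparison with 50% alone.
5. Do not impose a 75% null on PET-negative patients.

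The cost is wording and one descriptive table from data already planned, with no new procedures. The subgroup intervals will be wide: with about 18 patients per group if 36 split evenly, 12 of 18 progression-free has an exact 95% CI of 41-87%. The efficacy conclusion also becomes more cautious.

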2. STUDY OBJECTIVES

2.1 Primary Objective

The primary objective of this study is to:

- Evaluate safety and tolerability of nivolumab as maintenance therapy early after ASCT in patients with HL

2.2 Secondary Objectives

The secondary objective of this study is to:

- Evaluate PFS at 12 months post-transplant when nivolumab is administered as maintenance therapy in patients with HL after ASCT

2.3 Exploratory Objectives

The exploratory objectives of this study are to:

- Correlate efficacy of nivolumab when given as maintenance therapy after ASCT with PD-1 expression and other immune effector and regulatory cells
- Correlate positron emission tomography (PET)-computed tomography (CT) negativity with PFS

2.4 Endpoints

2.4.1 Safety Endpoints

- Type, incidence, severity, seriousness, and relatedness of AEs
- Laboratory abnormalities

CONFIDENTIAL

STUDY DRUG: NIVOLUMAB

SARAH CANNON DEVELOPMENT INNOVATIONS STUDY NUMBER:

FINAL PROTOCOL DATE: 07 FEB 2020

BMT 24

VERSION 7

- AEs leading to discontinuation

2.4.2 Efficacy Endpoint

- Progression-free survival

2.4.3 Additional Endpoint

- PET-CT negativity at 1 year post-transplant

3. STUDY PATIENT POPULATION AND DISCONTINUATION

3.1 Inclusion Criteria

Patients who will receive study drug must meet the following criteria in order to be included in the research study:

1. Patients 18 years of age and older with HL who have received auto-HSCT in the previous 45-180 days.
2. Complete response (CR), partial response (PR) or stable disease (SD) to salvage therapy prior to ASCT
3. High risk of residual HL post-ASCT, as determined by 1 of the following:
 - Positive PET scan defined by the Deauville scale 3-4 (Appendix C) and within 2 months of start of high-dose chemotherapy prior to ASCT
 - Refractory to frontline therapy
 - Relapse <12 months after frontline therapy
 - Relapse \geq 12 months after frontline therapy with extranodal disease
4. Eastern Cooperative Oncology Group (ECOG) Performance Status score of 0 - 1 (Appendix A).
5. Adequate hematologic function defined as all of the following:
 - Absolute neutrophil count (ANC) \geq 1000/ μ L
 - Hemoglobin (Hgb) \geq 8 g/dL (transfusions to reach this point are not permitted)
 - Platelets \geq 50,000/ μ L (transfusion is not permitted)
6. Adequate liver function defined as all of the following:
 - Alanine aminotransferase (ALT) and aspartate aminotransferase (AST) \leq 2.5 \times the upper limit of normal (ULN)
 - Total bilirubin \leq 1.5 \times ULN (unless the patient has Grade 1 bilirubin elevation due to Gilbert disease or a similar syndrome involving slow conjugation of bilirubin)
7. Adequate renal function defined as serum creatinine \leq 1.5 mg/dL (133 μ mol/L)

CONFIDENTIAL

STUDY DRUG: NIVOLUMAB

SARAH CANNON DEVELOPMENT INNOVATIONS STUDY NUMBER:

FINAL PROTOCOL DATE: 07 FEB 2020

BMT 24

VERSION 7

8. Females of childbearing potential must have a negative serum or urine pregnancy test result within 72 hours prior to the first dose of nivolumab and must agree to follow instructions for method(s) of contraception for the duration of treatment with nivolumab and for 7 months following their last dose of study drug (Appendix D). Females of non-childbearing potential are those who are postmenopausal greater than 1 year or who have had a bilateral tubal ligation or hysterectomy.
9. Male patients with female partners of childbearing potential and women patients of childbearing potential are required to use two forms of **acceptable** contraception, including one barrier method, during their participation in the study and for 7 months following last dose of study drug. Male patients must also refrain from donating sperm during their participation in the study and for 7 months following last dose of study drug (Appendix D).
10. Willingness and ability to comply with study and follow-up procedures.
11. Ability to understand the nature of this study and give written informed consent.

